Overall response rate (ORR) is defined as the proportion of patients with best overall response (BOR) of complete response (CR), complete response with incomplete marrow recovery (CRI), or partial response (PR), as assessed by investigators per IWCLL criteria (see VAY736Y2102-CSP-Appendix 1 for details) and will be calculated based on all response evaluations. The ORR will be calculated by dose level in dose escalation and by arm in dose expansion, and overall, and will be presented along with corresponding 90% exact confidence intervals (CI). Assessments taken after the start of alternative cancer therapy will be excluded.

Time to progression (TTP) is the time from start of treatment to the date of event which is defined as the first documented progression (defined as overall disease response assessment of PD) or death due to underlying cancer. If a patient has not had an event, time to progression is censored at the date of last adequate disease assessment. Assessments taken after the start of alternative cancer therapy will be excluded.

Median TTP (in months) with corresponding 95% CI, 25th and 75th percentiles (Brookmeyer and Crowley 1982, Klein and Moeschberger 1997) and Kaplan-Meier estimated probabilities (TTP rate) with corresponding 95% CIs (Greenwood's formula, Kalbfleisch and Prentice 1980) at several time points (3, 6, 12, 18 and 24 months) will be presented. The number (%) of progressions, deaths and patients censored will also be summarized.

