The overall disease responses of CR/CRi must stay the same until PD, with the exception of an UNK status. A patient who had a CR/CRi cannot subsequently have a lower status other than a PD, e.g. PR or SD, as this would imply a progression based on one or more disease component reappearing, in which case the status would become a PD.

Once an overall disease response of PR is observed, the PR response status must be maintained or improved over time until PD, with the exception of an UNK status. That is, after a single PR

the overall disease response should still be considered PR (or UNK) until PD is documented or the disease totally disappears in which case a CR/CRI assignment is applicable.

5.2.2.3.3 Establishing CR, CRI, PR and subsequent maintenance of CR, CRI, PR with no clinical evidence of progression

A full response evaluation, including assessments of peripheral blood, bone marrow, lymph node, liver, spleen and constitutional symptom, is required at the first time a CR or CRI is demonstrated ([Section 5.2.2.3.1](#)). Based on iwCLL response guidance, bone marrow aspirate/biopsy is not a required criterion for establishing PR. Additional bone marrow biopsies/aspirates may be recommended in the protocol.

Following initial achievement of CR, CRI or PR, if the patient has no evidence of PD as assessed on peripheral blood, lymph node, liver, spleen and constitutional symptoms, patients will be considered to have maintained a clinical CR, CRI or PR. The maintenance assessment of lymph node, liver and spleen can be done via physical exam or CT.

In order for the best overall disease response to be categorized as CR, CRI or PR, there must be no evidence of PD at a minimum of 8 weeks (56 days) after the initial achievement of CR, CRI or PR. Please note, if additional assessments (e.g. bone marrow, CT scan or lymph node biopsy/aspirate) are performed ([Section 5.2.2.3.1](#)) in the same evaluation for disease response evaluation purpose, they will also need to show remission status.

The onset date of CR, CRI or PR will then be derived as the evaluation date of the initial CR, CRI or PR assessment. If a patient satisfied CRI at one evaluation and later confirmed as a CR in the next evaluation, the patient will be considered as having confirmed CR.

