5.2.4.2 Time-to-event endpoints

General rule for the calculation of the time to event interval is:

Time to event = end date - start date + 1 (in days)

When no post-baseline response assessment is available, the date of *randomization/start of the treatment* will be used as end date (duration = 1 day), i.e., time to event variables will never be negative.

Often censoring time is determined based on date of adequate response assessment. Any response assessment is considered to be adequate if the assessment was performed and the outcome of the assessment was other than “not done” or “unknown”.

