5.2.4.3 Event and censoring date, sensitivity analysis

This section outlines the possible event and censoring dates for PD (Table 5-3), as well as addresses the issues of missing response assessments during the study. It is important that the protocol and analysis plan specify the primary analysis in detail with respect to the definition of event and censoring dates and also include a description of one or more sensitivity analyses to be performed. Using the draft FDA guideline on endpoints (Clinical Trial Endpoints for the Approval of Cancer Drugs and Biologics, April 2005) as a reference, the following analyses can be considered:

Table 5-3 Options for event dates used in TTP

Situation	Options	Outcome
	(1) = default unless specified differently in the protocol or analysis plan	
A No baseline or post-baseline assessment	(1) Date of randomization/start of treatment	Censor
B PD or death at scheduled assessment date or before next scheduled assessment	(1) Date of PD (or death) (2) Date of next scheduled assessment	Event
C1PD or death after exactly one missing assessment	(1) Date of PD (or death) (2) Date of next scheduled assessment ¹	Event
C2PD or death after two or more missing assessments	(1) Date of last adequate assessment ¹ (2) Date of next scheduled assessment ² (3) Date of PD (or death)	Censor Event Event

D	No PD and no death	(1) Date of last adequate assessment	Censor
E	Discontinuation of study treatment due to PD without documented PD, i.e. clinical PD based on investigator claim	(1) N/A	Ignored
F	New anti-cancer therapy given	(2) Date of discontinuation (visit date atEvent which clinical PD was determined)	
		(1) Date of last adequate assessment prior to start of new anti-cancer therapy	Censor
		(2) Date of new anti-cancer therapy	Event
		(3) Date of new anti-cancer therapy	Ignored
		(4) N/A	

¹ Date of the last adequate tumor assessment, is the date the last tumor assessment with overall lesion response of CR, PR, or SD before an event or censoring occurred.

² Date of next scheduled assessment is defined as the date of last adequate tumor assessment plus the protocol specified time interval for assessments.

The primary analysis and the sensitivity analyses must be specified in the Study Protocol. Clearly define if and why options (1) are not used for situations C,E, and (if applicable) F.

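### The SAP defines an adequate assessment for TTP in two conflicting ways, and the TTP-specific definition leaves out CRi

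*SAP*

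**What the plan says.** The main TTP text, SAP 2.8.1, reads: "If a patient has not had an event, time to progression is censored at the date of last adequate disease assessment". It lists no response categories, and neither does protocol 10.5.2. The term is filled in at two places in the SAP appendix.

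- SAP 5.2.4.2, the general rule for time-to-event endpoints, treats an assessment as "considered to be adequate if the assessment was performed and the outcome of the assessment was other than “not done” or “unknown". CRi meets this test.
- SAP 5.2.4.3, Table 5-3, footnote 1, which is specific to TTP, says the date of the last adequate assessment "is the date the last tumor assessment with overall lesion response of CR, PR, or SD before an event or censoring occurred". CRi is not in the list.

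Marker 1 is attached to option (2) of row C1, which is not a default, and to the default of row C2: "1) Date of last adequate assessment ¹". Row C2 covers PD or death following at least two missed assessments. Row D (neither PD nor death) and row F (new therapy) use the same term without a marker. The row F default is "1) Date of last adequate assessment prior to start of new anti-cancer therapy".

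CRi is a full response category in this SAP. Table 5-1 defines it, 2.8.1 counts it in the CR/CRi rate and the ORR, and 5.2.4.1 ranks it second for best overall response. Section 5.2.2.3.2 adds: "The overall disease responses of CR/CRi must stay the same until PD, with the exception of an UNK status".

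**The concern.** One derived date has two definitions, and they disagree only for CRi. Section 4, item 5 of the SAP brought in CRi and the TTP censoring rules in the same change, so the footnote probably was not aligned with the new category.

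The persistence rule makes the gap matter. A patient in CRi does not go back to PR or SD. Unless CRi later becomes CR, no visit from the first CRi onward is adequate under the footnote, and the last adequate date stays at the visit before the remission.

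Two programmers following the same SAP could therefore censor the same patient on different dates. The patients affected would be among the best responders. The TTP rates planned at 3, 6, 12, 18 and 24 months depend on who is still at risk.

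**Working it through.** The plan states no TTP estimate or event count that depends on the footnote, so there is no figure to reproduce. The check compares the two definitions and works out the censoring days.

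**Which outcomes count as adequate**

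| Outcome | 5.2.4.2 | Footnote 1 |
|---|---|---|
| CR, PR, SD | yes | yes |
| CRi | yes | no |
| Not done, unknown | no | no |

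PD is left out of the table because it is the event.

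**Inputs.** Cycles last 28 days (protocol 6.1.1). After C9D1, TTP follow-up is every 3 months for two years (protocol 7.1.2). The evaluations before that are taken as C4D1, C6D15 and C9D1, read from a visit table that is broken in the available text. A month is 30.4375 days.

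**Visit days.** Study day = (cycle − 1) × 28 + day of cycle.

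- C4D1: 3 × 28 + 1 = 85 (2.8 months)
- C6D15: 5 × 28 + 15 = 155 (5.1 months)
- C9D1: 8 × 28 + 1 = 225 (7.4 months)
- End of follow-up: 225 + 730 = 955 (31.4 months)

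**Row C2, where the marker is attached.** Take PR or SD at C6D15, CRi from C9D1 through day 225 + 365 = 590, two missed visits, then PD. Under 5.2.4.2 the patient is censored at day 590 (19.4 months). Under the footnote it is day 155 (5.1 months). The difference is 590 − 155 = 435 days (14.3 months). The C2 default censors under both definitions; only the date moves.

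**Row D, only if the footnote is read across.** Take a patient who stays in CRi without PD to day 955.

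| First CRi at | Censored at, footnote | Censored at, 5.2.4.2 | Days lost |
|---|---|---|---|
| C9D1 | 155 | 955 | 800 (26.3 months) |
| C6D15 | 85 | 955 | 870 (28.6 months) |
| C4D1 | 1 (no adequate post-baseline visit) | 955 | 954 (31.3 months) |

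**Effect on Kaplan-Meier, invented data.** Assume 20 patients: 4 first in CRi at C9D1 who never progress, 5 others with PD between days 300 and 500, and 11 followed to day 955 without PD.

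- 5.2.4.2: all 20 are at risk when the PDs begin, so the 24-month rate is 15/20 = 0.750.
- Footnote read across: the 4 CRi patients leave at day 155, so the rate is 11/16 = 0.688.

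With 2 to 6 CRi patients and 3 to 8 PDs, the fall at 24 months runs from 0.850 − 0.833 = 0.017 to 0.600 − 0.429 = 0.171.

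**The case against.** The strongest reply is that the SAP already contains the right rule. Section 5.2.4.2 makes CRi adequate, and SAP 2.8.1 and protocol 10.5.2 name no categories. Under those texts a CRi patient is censored at the last performed assessment and loses nothing. The footnote also fits this SAP poorly: it speaks of tumor assessment and lesion response, while the SAP's data item is overall disease response. CRi meets every CR criterion apart from a cytopenia unrelated to CLL, so CR in the footnote could be meant to cover it.

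This stands against two stronger readings that a reader might infer.

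- **That CRi patients who withdraw, switch therapy or finish follow-up are in fact censored before their remission.** The documents do not establish this. Those cases fall in rows D and F, which lack the marker, and no text says the footnote overrides 5.2.4.2.
- **That a PD after two or more CRi visits turns from an event into a censored time.** This would require performed CRi visits to be counted as missing. Rows C1 and C2 concern missing assessments, and nothing in the SAP tells the analyst to count them from the last adequate date as the footnote defines it.

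The reply does not remove the contradiction. The footnote is the TTP-specific text, it is attached to a default option, and it defines a term that rows D and F also use. Deriving one such date and using it in every row would be a natural way to program the table.

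**Conclusion.** The SAP contradicts itself on what counts as an adequate assessment for TTP. The conflict acts directly on the C2 default, where it moves the censoring date of a CRi patient to before the remission (435 days in the example). It could reach rows D and F, with a loss of up to about 26 months when CRi is first recorded at C9D1, but only if the footnote is read across to them.

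The sizes assume visits on schedule, CRi that does not improve to CR, and, for row D, two full years of follow-up. The SAP notes that the trial was endorsed for early termination, which may shorten follow-up. The number of CRi patients is not given. In an arm of the planned 20, each would be 1/20 = 5% of the arm; Arm B was closed to enrolment, so that arm may be smaller. The Kaplan-Meier figures illustrate the mechanism and do not predict the result.

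TTP is a secondary endpoint described without a test. The CR/CRi rate, ORR, DLT and safety analyses are not affected. The point should be corrected, but it does not threaten the trial's main conclusions.

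**What to change.** Change the list in footnote 1 of Table 5-3 to overall disease response of CR, CRi, PR or SD, or replace the list with a reference to 5.2.4.2. Apply that single definition in rows C1, C2, D and F. Add a sentence that a performed visit scored CRi is not a missing assessment when C1 and C2 are decided.

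The cost is a short SAP edit and the matching value in the derivation. No new data or patients are needed. SAP Section 1 already provides the route: an amendment before database lock, or an addendum after it.
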